9.4.2 Analysis of the Primary Efficacy Endpoint(s)

The primary endpoint is the score on the IES-R scale, which will be treated as a continuous variable. The primary outcome will be difference in IES-R score between the counseling groups at 3 months post disclosure. A linear regression model accounting for baseline differences in age, sex, and other relevant covariates will be used. Missing data will be handled in 2 ways: an analysis of available data, and using an imputed dataset. Imputation will be performed via multiple imputation using the MICE (Multivariate Imputation via Chained Equations) package. Imputation in this package uses linear and logistic regression to predict missing values. MICE assumes missing values are missing at random, and overall missingness pattern will be assessed using this package. Results will be reported as means with standard errors. Assumptions for each statistical model will be tested. Results will be analyzed using 2 approaches: data transformation and using nonparametric statistical tests, where necessary. Bonferroni correction will be used to correct for multiple-testing comparisons.

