9 STATISTICAL CONSIDERATIONS

9.1 Statistical Hypotheses

The primary hypotheses are: (1) Scores on the Genetics Knowledge Scale (GKS) will not differ between virtual pre-test genetic counseling and IMAGINE-PD methods, and (2) Scores on the genetic counseling satisfaction scale and test-related distress scale (IES-R) will not differ between telephone and telegenetic results disclosure methods. The primary analyses of knowledge will be measured by the GKS at 4 weeks after pre-test counseling; Satisfaction by the GCSS score between genetic counseling groups immediately after pretest and disclosure counseling; and test-related distress by the IES-R score at 3 months between post disclosure. The null hypothesis is that these methods differ.

Secondary hypotheses include IES-R at 6 months between genetic counseling groups, scores on affect, outcomes, and quality of life scales at 3 and 6 months.

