9.2 Sample Size Determination

The difference in IES-R between groups after genetic disclosure counseling is used to determine sample size. A clinically significant difference in IES-R score is not defined. Sample size is determined from previously reported normative data of the IES-R in a community sample of N=154 non-PTSD ex-service members, demonstrating a mean of 1.82 (SD=1.05).¹⁶ A range of equivalence limits, the difference in standard deviation beyond which a significant difference would be considered relevant, are demonstrated in **Table 3** at alpha = 0.05 and power of 80%.²⁵ A sample size of N=80/counseling group (divided between PD+gene+ (45%), PD+gene- (45%), and

PD-gene+ groups (10%)), with an expected attrition of 15-20%, would allow for analysis of the primary outcome at a conservative 0.5-0.75 SD equivalence limit, and allow genetic and PD-subgroup analysis.

8		8
Equivalence limit (SD)	Per Group	Total Sample Size
0.5	80	320
0.75	36	132
1	20	80

Table 3. Sample Size Estimates.

9.3 **Populations for Analyses**

Analyses will be conducted for all randomized participants *in the* Intention-to-Treat (ITT) Analysis Dataset, as well as the Per-Protocol Analysis Dataset defined a subset of the participants in the full analysis (ITT) set who complied with the protocol sufficiently to ensure that these data would be likely to represent the effects of study intervention according to the underlying scientific model (e.g., participants who complete the 3-month study visit).

Protocol 843748-
GET VIRTUAL PD
IMAGINE-PD

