9.4 Statistical Analyses

9.4.1 General Approach

Descriptive statistics will be presented as percentages for binary variables, and as means with standard deviations or median with IQR depending on the distribution of the data. For inferential tests, the Type I error will be set at 0.05 using two-tailed tests. Covariates will be determined based on their significance as independent predictors of outcome, although age and sex will be included in all models. Check on normality will be performed through data visualization as well as using appropriate statistical tests of normality (eg Shapiro-Wilks test). Transformation of non-normally distributed continuous variables will be performed, and models will be compared to non-transformed models using non-parametric tests.

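### The primary analysis in 9.4.1–9.4.2 is a two-tailed difference test between unnamed groups, with no contrast, single margin, interval rule or Bonferroni divisor, so it does not test the equivalence null in 9.1

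*Combined protocol and SAP*

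**What the plan says.** **Hypotheses (9.1).** For knowledge: "Scores on the Genetics Knowledge Scale (GKS) will not differ between virtual pre-test genetic counseling and IMAGINE-PD methods". For satisfaction and test-related distress, scores "will not differ between telephone and telegenetic results disclosure methods". The section closes with "The null hypothesis is that these methods differ". These are equivalence hypotheses about the two levels of each factor: pre-test mode for GKS, disclosure mode for GCSS and IES-R.

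**Sizing (9.2).** The trial is sized on IES-R with 80 per counseling group and 320 in total. The section admits that "A clinically significant difference in IES-R score is not defined" and says the sample, "with an expected attrition of 15-20%, would allow for analysis of the primary outcome at a conservative 0.5-0.75 SD equivalence limit". Table 3 lists 80, 36 and 20 per group at limits of 0.5, 0.75 and 1 SD, with totals of 320, 132 and 80.

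**Analysis (9.4.1–9.4.2).** "For inferential tests, the Type I error will be set at 0.05 using two-tailed tests". The primary analysis is a linear regression: "The primary outcome will be difference in IES-R score between the counseling groups at 3 months post disclosure". Results are given as means with standard errors, and Bonferroni correction is applied without stating the number of comparisons.

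**Primary endpoints.** The synopsis description names knowledge and outcomes scales plus IES-R. The synopsis endpoint list and section 3 name GKS, IES-R and GCSS after disclosure. Section 9.1 has "Satisfaction by the GCSS score between genetic counseling groups immediately after pretest and disclosure counseling", which adds a pre-test GCSS. Section 9.4.2 names IES-R alone.

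**Design label (4.1).** One sentence calls the design non-inferiority and also a test of equivalence.

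**The concern.** The hypothesis, the sample size and the analysis each describe a different comparison. Section 9.1 contrasts factor levels, 9.2 sizes cells, and 9.4.2 names neither. Elsewhere in the protocol a counseling group is one of four cells, so a reader of 9.4.2 could run a four-group comparison, pairwise cell comparisons or a main effect.

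The test is also of the wrong kind. A two-tailed difference test takes no difference as its null, and 9.1 takes a difference as its null. Failing to reject the first does not reject the second. Because the endpoint lists disagree, no Bonferroni divisor can be inferred either.

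What is at stake is the trial's main conclusion. With the contrast, margin, divisor and decision rule all open, they could be settled after the data are seen.

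**Working it through.** **Inputs.** From the documents: four cells of 80 allocated 1:1:1:1 (synopsis, 6.4); attrition 15–20%, alpha 0.05, power 80%, limits of 0.5–0.75 SD (9.2). Assumptions, because the plan gives no values: SD scaled to 1, true difference 0 for equivalence power, and a Bonferroni divisor of 3 as an illustration (GKS, IES-R and post-disclosure GCSS as one family).

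**Step 1. Reproduce Table 3.** For two one-sided tests (TOST) with true difference 0, n per group = 2 × [(z(1−α) + z(1−β/2)) / margin]². With α = 0.05 per side and 80% power, the z-values are 1.645 and 1.282.

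| Limit (SD) | n before attrition | n / 0.85 | Table 3 per group | 4 × per group | Table 3 total |
|---|---|---|---|---|---|
| 0.5 | 68.5 | 80.6 | 80 | 320 | 320 |
| 0.75 | 30.4 | 35.8 | 36 | **144** | **132** |
| 1 | 17.1 | 20.2 | 20 | 80 | 80 |

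The per-group figures are close to a comparison of two single cells by TOST at 0.05 per side with 15% attrition. A two-sided 0.05 calculation (or one-sided 0.025 non-inferiority) with 20% attrition is also close: 62.8/27.9/15.7 divided by 0.80 gives 78.5/34.9/19.6. Neither matches exactly, and 9.2 does not say whether attrition is already included, so this is an approximate inference. The 0.75 SD total breaks the fourfold pattern of the other two rows.

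**Step 2. Group sizes behind each contrast.** Each factor level in 9.1 pools two cells: 2 × 80 = 160 against 160. After 15–20% attrition, a cell has 80 × 0.80 to 0.85 = 64–68, and a factor level has 160 × 0.80 to 0.85 = 128–136.

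**Step 3. Difference test as written.** Probability of a non-significant two-sided t test when the true difference is 0.5 SD, the plan's smallest recommended limit (noncentral t, noncentrality 0.5 × √(n/2)):

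| n per group | alpha 0.05 | alpha 0.05/3 |
|---|---|---|
| 64 (cell) | 0.199 | 0.344 |
| 68 (cell) | 0.175 | 0.312 |
| 128 (factor level) | 0.021 | 0.057 |
| 136 (factor level) | 0.016 | 0.044 |

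If non-significance were taken as no difference, a smaller alpha would make that claim easier to reach. The size of the problem depends strongly on which contrast is meant.

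**Step 4. Equivalence power.** TOST at a 0.5 SD margin, true difference 0 (exact t, integrated over the pooled SD):

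| n per group | 0.05 per side | 0.05/3 per side |
|---|---|---|
| 64 (cell) | 0.757 | 0.500 |
| 68 (cell) | 0.791 | 0.554 |
| 128 (factor level) | 0.981 | 0.936 |
| 136 (factor level) | 0.986 | 0.952 |

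With a true difference of 0.1 SD, factor-level power is 94–95% at 0.05 per side and 85–87% at 0.05/3.

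**The case against.** The strongest reply is that the estimator is adequate. A regression reporting means and standard errors yields a confidence interval directly, and 9.2 supplies limits to set it against. That stands: the analysis could support an equivalence conclusion. What is missing is the rule, not the model.

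Second, 9.1's null can be read as implying an equivalence test, in which case non-significance fails to show equivalence and Bonferroni makes the claim harder. That is fair. A reader might infer that the plan intends to declare equivalence from a non-significant result, but no section says so. The error rates in Step 3 hold only under that reading. Still, 9.4 never adopts the equivalence test either.

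Three other stronger inferences are not supported:

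- **That 9.2 itself sets up 160 against 160.** It sizes cells of 80; the 160 follows only from combining 9.1 with the allocation.
- **That the trial is too small.** On the contrasts in 9.1, Step 4 shows ample power. The shortfall appears for comparisons of single cells at 0.5 SD once a divisor is assumed (50–55% at 0.05/3). At 0.75 SD, cells of 64–68 have 96–97% power with the same divisor.
- **That the attrition allowance in 9.2 contradicts replacement of withdrawn participants in 7.2.** Attrition can be expected and withdrawals still replaced, so this is not a clear conflict.

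**Conclusion.** The point holds as a mismatch between hypothesis and analysis. The test in 9.4.1–9.4.2 does not address the null in 9.1, and the contrast, single margin, interval rule and divisor are all unstated. The conflicting endpoint lists and the double design label in 4.1 leave the reader unable to fill the gaps.

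The consequence is conditional. If non-significance were read as equivalence, a true 0.5 SD difference would pass 17–20% of the time between cells (31–34% with divisor 3), but only about 2% (4–6%) between factor levels. Factor-level equivalence power at 0.5 SD is 98–99% at 0.05 per side and 94–95% at 0.05/3. These figures assume 15–20% attrition, equal variances and, for power, a true difference of zero; the divisor is illustrative.

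The Table 3 total of 132 should be 144. That is a slip with no effect on the planned 320.

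**What to change.** **In 9.4.2**, wording such as: *For each primary endpoint, one linear model will include pre-test mode and disclosure mode as main effects, with the planned covariates. The factor named in 9.1 for that endpoint will be tested, and the interaction will be reported descriptively. Equivalence will be concluded only if the confidence interval for the factor difference, at level 1 − 2 × the per-side alpha, lies wholly within the pre-stated margin for that endpoint. A non-significant difference is not evidence of equivalence.*

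**In 9.4.1**, state that the two-tailed difference test does not govern the primary equivalence analyses. Fix one per-side alpha, for example 0.05 (which roughly matches Table 3) divided by the number of primaries in a family. With three in one family this is 0.05/3 per side, and the interval level is 1 − 2 × 0.05/3 = 96.7%.

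**Margins.** Fix a single IES-R margin before data are seen and justify it, since 9.2 defines no clinically significant difference. Set the GKS and GCSS margins separately.

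**Consistency.** Use one list of primaries and one design label throughout. If non-inferiority is meant, give the one-sided rule and the reference mode, because the synopsis names telephone and 4.2 names virtual visits.

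**In 9.2**, restate power for the factor-level contrast and correct 132 to 144.

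**Cost.** Wording, a recalculated table and an argued margin per endpoint; no extra participants or visits. The downside is that factor-level estimates assume no material interaction between pre-test and disclosure mode.

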3 STUDY OBJECTIVES AND ENDPOINTS

Outcomes to be studied include cognitive and affective outcomes, which will be measured via questionnaire-based scales (See **Table 2**). The questionnaires will be administrated electronically utilizing REDCap, a secure online data collection tool. Outcome measures will be collected at multiple time points throughout the study; however, the primary outcomes include Genetics Knowledge Scale at 4 weeks after pre-testing counseling, Genetics Counseling Satisfaction Scale immediately after disclosure counseling, and the Revised Impact of Events Scale 3 months after genetic results disclosure. A data monitoring plan will be in place to ensure patient safety.

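### Replacing single-step Bonferroni in 9.4.2 and 9.4.3 with Holm's step-down test is a nearly costless improvement, worth up to about 12 points on three primary equivalence claims at a 0.5 SD limit and nothing at 0.75 SD on the factorial comparison

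*Combined protocol and SAP*

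**What the plan says.** Section 9.4.2 (primary) and section 9.4.3 (secondary) contain the same sentence: "Bonferroni correction will be used to correct for multiple-testing comparisons". Neither says which tests form the family or what the divisor is. No step-down, hierarchical or gatekeeping procedure appears anywhere in the document.

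The number of primary claims is not consistent. Section 3 says "the primary outcomes include Genetics Knowledge Scale at 4 weeks after pre-testing counseling, Genetics Counseling Satisfaction Scale immediately after disclosure counseling" and then adds IES-R at 3 months. The synopsis, Table 2 and section 9.1 also treat all three scales as primary, and 9.1 measures GCSS after pre-test counseling as well as after disclosure. Section 9.4.2, however, names IES-R alone as the primary endpoint.

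The tests are also described in two ways. Section 9.1 sets an equivalence-type null, namely that the methods differ. Section 9.4.1 says "For inferential tests, the Type I error will be set at 0.05 using two-tailed tests", and 9.4.2 describes a regression for the difference between groups. No equivalence test is specified in 9.4.

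Section 9.2 sizes the trial on IES-R "at alpha = 0.05 and power of 80" percent, for a "conservative 0.5-0.75 SD equivalence limit". It gives "A sample size of N=80/counseling group" "with an expected attrition of 15-20" percent.

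**The concern.** Bonferroni holds every endpoint to alpha/k, whatever the other endpoints show. Holm starts at the same alpha/k for the smallest p-value, then tests the next at alpha/(k-1), and so on. It controls the familywise error rate at the same level without any assumption about correlation, and it cannot lose a rejection that Bonferroni would have made.

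If the trial wants positive conclusions on several scales, single-step Bonferroni therefore gives up some power on the second and third endpoints and gains no error control in return. The sizing in 9.2 appears to carry no allowance for a multiplicity correction, so any avoidable loss falls on the planned numbers.

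**Working it through.** **Inputs from the plan.** 80 per counseling group, four groups, 1:1:1:1 (9.2, 6.4), so 160 per factor level. With 15-20% attrition this leaves 136 to 128 completers per factor level, or 68 to 64 per single group. Equivalence limit 0.5 to 0.75 SD, alpha 0.05 (9.2). The IES-R SD cancels because the limit is in SD units.

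**Assumptions not in the plan.** True difference 0, three claims (k = 3), two one-sided tests (TOST) with a familywise level of 0.05 per side, normal approximation, independent statistics unless stated.

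**Reproducing Table 3.** n = 2 × [(z(0.95) + z(0.90)) / limit]². At 0.5 SD this is 2 × [(1.645 + 1.282)/0.5]² = 68.5, so 69. At 0.75 and 1 SD it gives 31 and 18. Adding 15% gives 69 × 1.15 = 79.4, 31 × 1.15 = 35.7 and 18 × 1.15 = 20.7, against the table's 80, 36 and 20. The planned 80 is therefore consistent with the 0.5 SD limit at unadjusted alpha.

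**Power per claim at level a.** P(a) = 2Φ(limit/SE − z(1−a)) − 1, with SE = √(2/n). For n = 128, SE = 0.125 and 0.5/SE = 4:
- A = P(0.05/3) = 2Φ(4 − 2.128) − 1 = 0.939
- B = P(0.05/2) = 2Φ(4 − 1.960) − 1 = 0.959
- C = P(0.05) = 2Φ(4 − 1.645) − 1 = 0.981

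**All three claims established.**
- Bonferroni: A³ = 0.827.
- Holm needs the ordered p-values to be at most 0.05/3, 0.05/2 and 0.05. With y = B − A and w = C − B, the probability is A³ + 3A²y + 3A²w + 3Ay² + 6Ayw = 0.827 + 0.052 + 0.060 + 0.001 + 0.003 = 0.944 (unrounded terms).
- A simulation with GCSS and IES-R correlated 0.2 gives 0.829 and 0.944, and per-endpoint power of 0.939 and 0.979.

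**At least one claim established.** 1 − (1 − A)³ = 0.9998 under both methods, because both test the smallest p-value at alpha/3.

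**Other settings (chance of all three, Bonferroni → Holm, 0.05 per side):**

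| Comparison | n | 0.5 SD | 0.75 SD |
|---|---|---|---|
| Factor level, 20% attrition | 128 | 83% → 94% | about 100% either way |
| Factor level, 15% attrition | 136 | 87% → 96% | about 100% either way |
| Factor level, no attrition | 160 | 94% → 99% | about 100% either way |
| Single group, 20% attrition | 64 | 14% → 40% | 90% → 97% |
| Single group, 15% attrition | 68 | 18% → 46% | 93% → 98% |

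**Sensitivity at 0.5 SD on factor levels:**
- 0.025 per side, n = 128: 71% → 88%.
- True difference 0.1 SD, n = 128: 62% → 82%.
- Common correlation 0.8, n = 136: 91% → 97%.
- Four claims (GCSS counted at both times, as 9.1 allows), n = 136: 78% → 95%.
- One claim: no change.

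**The case against.** Bonferroni is a valid method, so this is a choice between valid analyses. A reader might infer that the plan gives away a clear share of its chance of establishing its primary claims, whatever else is decided. The documents do not support that, for five reasons.

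1. The limit is a range. At its upper end, 0.75 SD, Bonferroni already establishes all three claims almost surely on the factorial comparison, and Holm adds nothing.
2. Section 9.4.2 names one primary endpoint. On that reading there is no loss across primary endpoints, and the correction there might refer to contrasts among the four counseling groups. The synopsis, section 3, Table 2 and 9.1 point the other way, but the conflict is in the plan.
3. The plan never says that all three claims must succeed. If it did, no adjustment would be needed: each claim at 0.05 gives 0.981³ = 94.5%, practically the same as Holm's 94.4%. If the claims stand separately, the relevant gain is the per-endpoint one, 94% to 98%.
4. The figures assume equivalence tests, which 9.4 does not specify. Under the two-tailed difference tests it describes, Holm would make it easier to declare a difference, which does not help the 9.1 claims.
5. The figures concern the primary claims only. No gain has been computed for the secondary family in 9.4.3.

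All five stand, and they limit the size of the point. They do not affect its basis: at the same familywise error rate, Holm never rejects less than Bonferroni.

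**Conclusion.** The point holds as a cheap improvement, not as an error in the plan. Three separate primary equivalence claims, TOST with a familywise level of 0.05 per side, true difference 0 and a 0.5 SD limit give these gains on factor levels: 9 to 12 points in the chance of establishing all three after 15-20% attrition, and 4 points per endpoint (94% to 98%) at 128 completers. If single groups were compared at 0.5 SD, the gain in the chance of all three would be 26 to 28 points after attrition.

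The gain is nil at 0.75 SD on factor levels and nil if IES-R is the sole primary claim. The chance of at least one success is the same under both methods. For the secondary endpoints only the general fact applies, that Holm is never less powerful.

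**What to change.** In 9.4.2 and 9.4.3, replace Bonferroni correction with Holm step-down correction within each family. For the primary equivalence claims, apply it to each endpoint's TOST p-value, the larger of the two one-sided p-values.

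Reconcile 9.4.2 with the synopsis, section 3, Table 2 and 9.1, so that the primary family is the one in 9.1. State whether GCSS after pre-test counseling belongs to it.

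The Holm wording changes one phrase in each of two sections and needs no new data or participants. For the primary claims the benefit also requires 9.4 to specify the equivalence test and its limit, which the 9.1 hypotheses call for in any case. The one drawback is that Holm decisions do not map onto a simple set of simultaneous confidence intervals, so each endpoint's interval should be reported separately from the step-down decision.

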9.4.3 Analysis of the Secondary Endpoint(s)

All secondary outcome variables will be treated as continuous variables. The hypotheses will be difference between counseling method groups at all study timepoints. A linear regression model accounting for baseline differences in age, sex, and other relevant covariates will be used. Missing data will be handled in 2 ways: an analysis of available data, and using an imputed dataset. Results will be reported as means with standard errors. Assumptions for each statistical model will be tested. Results will be analyzed using 2 approaches: data transformation and using nonparametric statistical tests, where necessary. Bonferroni correction will be used to correct for multiple-testing comparisons.

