2.3.3 Assessment of Potential Risks and Benefits

The risk of causing significant depression, anxiety, or suicidality as a result of genetic counseling or testing are very low. Genetic counselors are trained to recognize unsafe conditions and changes in affect related to genetic testing. They will follow established clinical pathways and will alert the PI with concerns. Additionally, secondary outcomes include scales of depression, anxiety, distress, and suicidality, which will be monitored by the study team, overseen by the PI.

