9.4.4 Safety Analyses

No statistical analysis will be performed on safety endpoints. The Columbia Suicidality Rating Scale will be monitored at each visit. Any concerning result will trigger appropriate referral for mental health counseling or medical care.

Protocol 843748-
GET VIRTUAL PD
IMAGINE-PD

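### GDS and STAI are analysed only as Bonferroni-corrected difference tests with no interval promised, and adverse events are not compared between counseling modes, so non-significance cannot support safety

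*Combined protocol and SAP*

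**What the plan says.** Section 2.3.3, on the risk of depression, anxiety and suicidality, states that "secondary outcomes include scales of depression, anxiety, distress, and suicidality, which will be monitored by the study team". GDS and STAI are the depression and anxiety scales in Table 2. The Schedule of Activities collects both at Visits 1, 3 and 4.

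For secondary outcomes, section 9.4.3 states: "The hypotheses will be difference between counseling method groups at all study timepoints". It adds "Bonferroni correction will be used to correct for multiple-testing comparisons" and "Results will be reported as means with standard errors". The model adjusts for age, sex and unspecified relevant covariates. No margin, no interval for the difference and no list of the tests in the Bonferroni family is given. Section 9.1 places the secondary comparisons at two visits: "scores on affect, outcomes, and quality of life scales at 3 and 6 months", together with IES-R at 6 months. Section 9.4.1 says "the Type I error will be set at 0.05 using two-tailed tests".

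Section 9.4.4 opens: "No statistical analysis will be performed on safety endpoints". Adverse events are nevertheless reviewed at Visits 1 to 4 (Schedule of Activities), with severity, relatedness and seriousness recorded (section 8.2.4). No tabulation of them by counseling group is planned.

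**The concern.** For the primary outcomes, section 9.1 takes a difference between methods as the null, so similarity has to be demonstrated. For GDS and STAI the burden is reversed: similarity is the default and a difference has to be demonstrated. On a harm scale the costly error is the miss, and Bonferroni raises the chance of a miss as the family grows.

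The trial is presented as a route to safe counseling at scale, and section 2.3.1 says that no known risks differ between modes. This trial can check that statement. A table of non-significant corrected p-values would not, because it does not show how large a worsening remains compatible with the data. Adverse events would add nothing to the comparison, although they are already collected.

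**Working it through.** **Inputs from the plan.** Two-sided alpha 0.05 (9.4.1). 80 per cell, 320 in total, attrition 15% to 20% (9.2). 1:1:1:1 allocation to a two-by-two factorial (6.4), so each factor compares 160 with 160. After attrition this is 160 × 0.85 = 136 or 160 × 0.80 = 128 per level, and 80 × 0.80 = 64 per cell.

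**The plan's own figure.** Table 3 gives 80 per group at 0.5 SD. A two-sided difference test at 80% power (t version) needs 64 per group, and 64/0.80 = 80. An equivalence calculation at one-sided 0.05 needs 69, and 69/0.85 = 81.2, rounded up to 82. Either route is close; the plan does not say which was used. The sizing concerns IES-R. No margin or SD is given for GDS or STAI, so effects below are in SD units.

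**Assumed Bonferroni families.** The plan defines none.
- k = 4: GDS and STAI at two visits, one factor.
- k = 8: GDS and STAI at two visits for both factors, or GCOS, GDS, STAI and PDQ-39 at two visits for one factor.
- k = 16: those four scales at two visits for both factors.

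Counting 6-month IES-R or C-SSRS would enlarge the family.

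**Power for one test, factor main effect, 128 per level.** SE = sqrt(2/128) = 0.125 SD. Power = Φ(d/SE − z), where z is the upper 0.025/k normal quantile. For d = 0.3, d/SE = 2.4; for d = 0.5, d/SE = 4.0.

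| k | z | 0.2 SD | 0.3 SD | 0.4 SD | 0.5 SD |
|---|---|---|---|---|---|
| 1 | 1.960 | 36% | 67% | 89% | 98% |
| 4 | 2.498 | 19% | 46% | 76% | 93% |
| 8 | 2.734 | 13% | 37% | 68% | 90% |
| 16 | 2.955 | 9% | 29% | 60% | 85% |

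Power is 50% at d = z × SE: 0.31 SD for k = 4, 0.34 SD for k = 8 and 0.37 SD for k = 16. With 136 per level, the 0.3 SD column becomes 70%, 49%, 40% and 31%.

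**If groups means single cells.** Section 9.4.3 does not say whether factor levels or the four cells are compared. With 64 per cell, SE = sqrt(2/64) = 0.177 SD. Power at 0.5 SD is then 81% uncorrected and 63%, 54% and 45% for k = 4, 8 and 16.

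**If the Visit 1 score is a covariate.** Assume a correlation of 0.5 with the outcome (no figure is in the plan). SE = 0.125 × sqrt(1 − 0.25) = 0.108 SD. Power at 0.3 SD is then 79% uncorrected and 61%, 51% and 43% for k = 4, 8 and 16.

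**What an interval would show.** The unadjusted 95% half-width is 1.96 × 0.125 = 0.245 SD with 128 per level and 0.238 SD with 136, before any covariate gain.

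**The case against.** Multiplicity control over secondary endpoints is a conventional choice, and it changes thresholds, not estimates or standard errors. The scales are prespecified. Dropping the correction would trade missed harms for false alarms. This stands, and it is why the fix places intervals beside the adjusted tests instead of removing the tests.

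A reader might infer that any real harm would probably be reported as no difference. The figures do not support that. At 0.5 SD, the plan's lower IES-R equivalence limit, main-effect power stays at 85% to 93% for the assumed families. Adjusting for the Visit 1 score would raise power further; sections 9.4.1 and 9.4.3 allow it without committing to it.

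A reader might also infer that the plan contains no estimate of harm by counseling group. That is too strong. IES-R distress is a primary between-group outcome and the basis of the sample size, although section 9.4.2 also describes a Bonferroni-corrected analysis of difference for it. GDS and STAI means with standard errors are planned, from which an approximate interval could be built. The absence is complete only for adverse events.

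Finally, section 2.3.3 speaks of monitoring by the study team. It does not say that the scales will establish whether counseling or testing causes depression, and since every arm is tested, no comparison of modes could show an effect of testing. Individual protection exists: C-SSRS review with referral (9.4.4), adverse event review (8.2.4) and an independent safety monitor (10.1.5). These protect participants, but none compares the modes.

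**Conclusion.** The concern holds in a limited form. The plan tests GDS and STAI only for difference under an undefined Bonferroni family, promises neither baseline adjustment nor an interval, and forgoes any comparison of adverse events between modes. Non-significance on these scales would not be evidence of safety.

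The exposure is to small-to-moderate harm. At 0.3 SD in a factor main effect, the chance of a miss rises from 33% uncorrected to about 54%, 63% or 71% with 4, 8 or 16 tests. Harms of 0.5 SD would usually be detected, unless single cells are compared, where the odds come closer to even.

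These figures assume the stated family sizes, 20% attrition, roughly normal outcomes and no covariate gain. The documents do not define what size of harm on GDS or STAI would matter.

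**What to change.** **Section 9.4.3.**
- Report the GDS and STAI differences for each factor at 3 and 6 months, from models that include the Visit 1 score.
- Report the 6-month IES-R difference for each factor without a baseline term, since none is collected.
- Give each an unadjusted 95% confidence interval alongside any Bonferroni-adjusted test, and label the intervals as not multiplicity-controlled.
- State that non-significance on these scales is not evidence of safety.

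**Section 9.4.4.** Replace the opening sentence with descriptive counts, by arm and by factor level, of participants with any adverse event, any serious adverse event, and withdrawal due to an adverse event. Add risk differences with 95% confidence intervals and no hypothesis test.

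**Reconcile the two sections.** C-SSRS is listed as a secondary outcome, so section 9.4.3 would test it as a continuous variable, while section 9.4.4 bars analysis of safety endpoints and then discusses C-SSRS.

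**Cost.** SAP wording and one extra table, with no new data: the Visit 1 scores, the adverse event records and the withdrawal reasons (section 7.2) are already collected. The downside is that some unadjusted intervals will exclude zero by chance, which the labelling has to make plain.
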